13.4. Reporting Adverse Events

The Investigator will notify the Sponsor of an adverse event by e-mail, facsimile, or telephone as soon as possible and no later than 24 hours from discovery for any serious /significant adverse events, and 2 days from discovery for any non-significant adverse event. In addition, a written report will be submitted by the Principal Investigator to the IEC/IRB according to their requirements (section 13.4.2). The report will comment whether the adverse event was considered to be related to the test article, study treatment or study procedures.

13.4.1. Reporting Adverse Events to Sponsor

Serious/Significant Adverse Events

The Investigator will inform the sponsor of all serious/significant adverse events occurring during the study period as soon as possible by e-mail or telephone, but no later than 24 hours following discovery of the event. The Investigator is obligated to pursue and obtain information requested by the Sponsor in addition to that information reported on the eCRF. All subjects experiencing a serious/significant adverse event must be followed up and all outcomes must be reported.

When medically necessary, the Investigator may break the randomization code to determine the identity of the treatment that the subject received. The Sponsor and study monitor should be notified prior to unmasking the test articles.

In the event of a serious/significant adverse event, the Investigator must:

- Notify the Sponsor immediately.
- Obtain and maintain in the subject’s records all pertinent medical information and medical judgment for colleagues who assisted in the treatment and follow-up of the subject.
- Provide the Sponsor with a complete case history which includes a statement as to whether the event was or was not related to the use of the test article.

Clinical Study Protocol
Johnson & Johnson Vision Care, Inc.

- Notify the IEC/IRB as required by the IEC/IRB reporting procedure according to national regulations.

Unanticipated (Serious) Adverse Device Effect (UADE)

In the event of an Unanticipated (Serious) Adverse Device Effect (UADE), the Investigator will submit a report of the UADE to the Sponsor and IEC/IRB as soon as possible, but no later than 24 hours after the Investigator first learns of the effect. This report is in addition to the immediate notification mentioned above.

The Sponsor must conduct an evaluation of the UADE and must report the results of the evaluation to FDA, the IEC/IRB and participating Investigators within 10 working days after the Sponsor first receives notification of the effect.

Non-Serious Adverse Events

All non-serious adverse events, including non-serious adverse device effects, will be reported to the sponsor by the Investigator no later than 2 days from discovery.

13.4.2. Reporting Adverse Events to the Responsible IEC/IRB and Health Authorities

Adverse events that meet the IEC/IRB requirements for reporting must be reported within the IEC/IRB's written guidelines. Each clinical site will refer to and follow any guidelines set forth by their Approving IEC/IRB. Each clinical site will refer to and follow any guidelines set forth by their local governing Health Authorities.

The Sponsor will report applicable Adverse Events to the local health authorities according to the written guidelines, including reporting timelines.

13.5. Event of Special Interest

None.

13.6. Reporting of Pregnancy

Subjects reporting pregnancy (by self-report) during the study will be discontinued after the event is recorded as an Adverse Event. Once discontinued, pregnant participants and their fetuses will not be monitored for study related purposes. Pregnant participants are not discontinued from contact lens or solution related studies for safety concerns, but due to general concerns relating to pregnancy and contact lens use. Specifically, pregnant women are discontinued due to fluctuations in refractive error and/or visual acuity that occur secondary to systemic hormonal changes, and not due to unforeseen health risks to the mother or fetus.

14. STATISTICAL METHODS

14.1. General Considerations

Statistical Analysis will be undertaken by the sponsor or under the authority of the sponsor. A general description of the statistical methods to be implemented in this clinical trial is outlined below. More details will be included in the stand-alone Statistical Analysis Plan (SAP). The SAP will be developed and finalized prior to database lock.

All data summaries and statistical analyses will be performed using the SAS software Version 9.4 SAS Institute, Cary, NC⁷. Throughout the analysis of data, the results for each subject/eye will be used when available for summarization and statistical analysis. For the analysis of co-primary safety endpoints, unscheduled visits will be summarized separately and will not be excluded from the statistical analysis. However, for the analysis of co-primary efficacy endpoints and secondary endpoints, unscheduled visits will be summarized separately and excluded from the statistical analysis.

Summary tables (descriptive statistics and/or frequency tables) will be provided for all baseline variables, efficacy variables and safety variables as appropriate. Continuous variables will be summarized with descriptive statistics

Clinical Study Protocol
Johnson & Johnson Vision Care, Inc.

(n, mean, standard deviation(SD), median, minimum and maximum). Frequency count and percentage of subject.s or eyes within each catego1y will be provided for categorical data.

Summaries will be presented by separately for each time point (baseline, fitting and 1-week follow-up) and will be perfo1med separately by completion status (Safety Population, Per-Protocol Population or Intent-to-treat, when appropriate).

14.2. Sample Size Justification

This study was designed and powered to test for superiority of the test lens after 1-week of lens wear with respect to the following: distance monocular HLHC visual acuity (logMAR), subjective vision scores, toric lens orientation, and rotational stability. This study was also powered to test superiority of the test lenses with respect to grade 3 or higher slit lamp findings and percentage of eyes with acceptable lens fit. Additionally, this study was also powered to test for superiority with respect to CLUE Comfort and Handling scores after 1-week of lens wear. The described alpha adjustment is also factored into these estimations of sample size and power.

The sample size for co-prima1y efficacy endpoints was estimated to achieve a minimum statistical power of 90% for distance monocular visual acuity (logMAR), toric lens orientation, rotational stability, and CLUE Vision scores using a 2-sided type I eITor rate of 5%. Co-prima1y safety endpoints (grade 3 or higher SLFs and acceptable lens fitting) were estimated to achieve a minimum statistical power of 99% with 95% central posterior credible interval.

A summa1y of historical studies utilized in the sample size calculation are summarized in Table 7 below, while Table 8 summarizes the historical data for the test lens by endpoint.

Table 7: Historical Studies Utilized for Sample Size Calculations

Study Number	Design	Sample Size	Number in Safety	Number in PP
4	2x3	Feasibility	145	144
	2x3	Conformation	126	26

PP: Per-Protocol

Table 8: Historical Data by Endpoint - Test Lens

Endpoint Type	Endpoint	Data Type	Value
*Primary Safety	Grade 3 + SLFs (Adverse Event)	Rate	0%
	Acceptable Lens Fitting		100%
**Primaiy Efficacy	Distance Monocular Visual Acuity (logMAR)	Mean (SD)	-0.115 (0.0769)
	Absolute Toric Rotation 10°		97.5%
	Lens Stability with Blinks 5°		100%
	CLUE Vision Scores		67.4 (19.67)
**Secondary	CLUE Handling Scores	Mean (SD)	65.4 (21.50)
	CLUE Comfort Scores		67.9 (21.50)

SD=Standard Deviation

*Summaries for the primaiy safety endpoints were provided for the safety population; all available data was included

**Summaries for primary efficacy and seconda1y endpoints were provided for the per-protocol population at the 1-week follow-up evaluation.

Clinical Study Protocol

CR-6521, v 3.0

■ JJV C CONFIDENTIAL

**Clinical Study Protocol
Johnson & Johnson Vision Care, Inc.**

Co-Primary Safety Endpoint Sample Size Calculations:

Grade 3 or Higher Slit Lamp Findings (SLFs)

Grade 3 or Higher SLFs related to study lens wear will be converted to a binary response as $YY = 1$, if a subject eye has a clinically significant SLF, and $YY = 0$ otherwise, for analysis purposes. From the historical data there was *none or an extremely low rate* ($< 1\%$) for clinically significant SLFs (Grade 3 or higher) for the test lens. Assuming a correlation of 0.70 between left and right eyes within the same subject, a total of 5000 replicating trials were simulated with a reference rate of 2% (worse-case scenario). Given the rare event binary outcome of slit lamp findings, each replicated sample was analyzed using a Bayesian beta-binomial model with correlated binary data (Diniz et al; 2010).⁸ For each simulated trial, the upper bound of the 95% central posterior credible interval constructed for the percentage of grade 3 or higher SLFs for the test lens was compared to a margin of 5%. With the proposed sample size, at least 99% of the estimated 95% credible intervals had the upper bound below 5%.

Acceptable Lens Fitting

Acceptable lens fitting will be converted to a binary response as $YY = 1$, if a subject eye has acceptable lens fitting, and $YY = 0$ otherwise, for analysis purposes. As indicated in the historical data of these lenses there was an extremely high rate ($> 99\%$) acceptable lens fitting for the test lens. Assuming a correlation of 0.70 between left and right eyes within the same subject, a total of 5000 replicating trials were simulated with a reference rate of 99% (worse-case scenario). Given the rare event binary outcome of $Y=0$ (unacceptable lens fitting), each replicated sample was analyzed using a Bayesian beta-binomial model with correlated binary data (Diniz et al; 2010).⁸ For each simulated trial, the upper bound of the 95% central posterior credible interval constructed for the percentage of acceptable lens fittings for the test lens was compared to a margin of 80%. With the proposed sample size, at least 99% of the estimated 95% credible intervals had the lower bound above 80%.

Co-Primary Efficacy Endpoint Sample Size Calculations:

Distance Monocular Visual Acuity (logMAR) and CLUE Vision Scores

Sample size calculations for visual acuity and vision scores were carried out separately using one-sided, one-sample mean t-test, with a type I error rate of 5% for each hypothesis. The hypothesis regarding visual acuity was powered to 99%, while the hypothesis for CLUE Vision scores was powered to 91%. Sample size calculations were performed using the *One-Sample T-Tests for Superiority by a Margin* procedure in Power Analysis & Sample Size (PASS2021) software Version 21.0.6 (NCSS LLC, Kaysville UT).⁹ Table 9 below, displays sample size estimates by endpoint.

Toric lens orientation and rotational stability

Sample size estimates for toric lens orientation and rotational stability were calculated using the same technique. Both endpoints are testing against an 80% threshold and have an event rate greater than 97%. A reference rate of 97.5% was used for toric lens orientation, while a worst-case scenario of 98% was used for rotational stability.

Toric lens orientation and rotational stability will be converted to a binary response as $YY = 1$ if a subject eye has absolute toric lens orientation $\leq 10^\circ$ (rotational stability: $Y=1$ if a subject eye has lens stability with blinks $\leq 5^\circ$) and $YY = 0$ otherwise, for analysis purposes. As indicated historical data of these products there was an extremely high rate ($> 97\%$) for both toric lens orientation and rotational stability for the test lens. Assuming a correlation of 0.70 between left and right eyes within the same subject, a total of 5000 replicating trials were simulated with a reference rate of 97.5% for toric rotation and 98% for rotation stability (worse-case scenario). Given the rare event binary outcome of $Y=0$, each replicated sample was analyzed using a Bayesian beta-binomial model with correlated binary data (Diniz et al; 2010).⁸ For each simulated trial, the upper bound of the 95% central posterior credible interval constructed for the percentage of acceptable lens fittings for the test lens was compared to a margin of 80%. With the proposed sample size, at least 99% of the estimated 95% credible intervals had the lower bound above 80%.

Secondary Endpoint Sample Size Calculations:

Clinical Study Protocol
Johnson & Johnson Vision Care, Inc.

CLUE Handling and Comfort Scores

Sample size calculations for handling and comfort scores were calculated separately using one-sided, one-sample mean t-test, with a type I error rate of 2.5% for each hypothesis. To preserve the overall study power, each endpoint was powered to 99%. Sample size calculations were performed using the *One-Sample T-Tests for Superiority by a Margin* procedure in Power Analysis & Sample Size (PASS2021) software Version 21.0.6 (NCSS LLC, Kaysville UT).⁹

Table 9 below, displays sample size estimates by endpoint. As indicated below, co-primary safety endpoints were powered ~99% individually yielding a combined power of ~98%. With respect to co-primary efficacy, each hypothesis, except for CLUE Vision (powered to 91%) was powered to ~99%, which provided a combined power of ~88%. Therefore, the overall combined study power for co-primary safety and co-primary efficacy hypotheses is ~86% and is considered reasonable to support any conclusions from these analyses. Furthermore, secondary endpoints were powered to achieve at least 99% statistical power. This was considered to have a minimal impact on overall study power because of the multibranch gate keeping approach being implemented.

Table 9: Sample Size Estimates for Co-Primary Safety, Efficacy and Secondary Endpoints

Endpoint Type	Endpoint	Test Type	Sample Size	Power (%)
Primary Safety	Grade 3 or Higher SLFs (5%)	Statistically less than (5%)	100	99
	Acceptable Lens Fitting (%)	Statistically greater than (80%)	100	99
Primary Efficacy	Distance (4m) Monocular Visual Acuity (logMAR)	Superiority (0.00)	9	99
	Absolute Toric Rotation < 100	Statistically greater than (80%)	40	99
	Lens Stability with Blinks 5°	Statistically greater than (80%)	100	99
	CLUE Vision Scores	Superiority (62)	144	91
Secondary	CLUE Handling Scores	Superiority (61)	135	97
	CLUE Comfort Scores	Superiority (58)	135	97

While only a total of 144 subjects are required to complete the study based on the sample size calculations, the target enrollment is approximately 180 subjects with a target completion of at least 165 subjects. Data collected from this study may be utilized to perform a meta-analysis at a later date, therefore, the target completion for this study was increased to 165 subjects to accommodate this possibility.

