2.3. Hypotheses

Co-Primary Safety Hypotheses:

1. The percentage of eyes with one or more clinically significant, study-lens related, slit-lamp findings (Grade 3 or 4) following wear of the test lenses will be less than 5%.
2. At least 80% of lens fits will be acceptable at the dispensing visit.

Both co-primary *safety* hypotheses must be met in order to test any co-primary *efficacy* hypotheses.

Co-Primary Efficacy Hypotheses:

1. After approximately 1-week of wear, the mean monocular, high-luminance, high-contrast distance visual acuity for the test lens will be lower than 0.00 logMAR (equivalent to 20/20 Snellen visual acuity).
2. Following lens settling (at least 15 minutes) at the dispensing visit, at least 80% of lens fits will have absolute rotation less than or equal to 10 degrees.
3. Following lens settling (at least 15 minutes) at the dispensing visit, at least 80% of lens fits will have lens rotational stability with blink less than or equal to 5 degrees.
4. After approximately 1 week of wear, the mean overall CLUE™ Vision score for the test lens will be statistically greater than 62 points.

All safety and efficacy co-primary hypotheses must be satisfied in order to meet the study objectives and to test any secondary hypotheses.

Secondary Hypotheses:

1. After approximately 1 week of wear, the mean overall CLUE™ Handling score for the test lens will be greater than 61 points with 95% statistical confidence.
2. After approximately 1 week of wear, the mean overall CLUE™ Comfort score for the test lens will be greater than 58 points with 95% statistical confidence.

Clinical Study Protocol
Johnson & Johnson Vision Care, Inc.

Exploratory Hypotheses:

1. After approximately 1 week of wear, the test lens will be non-inferior to the control lens with respect to at least one of the following subjective questionnaire items asked at the follow-up visit:
 - a. Ability to see comfortably while driving during the day
 - b. My vision was clear enough to allow me to drive at night
 - c. Reduction in the feeling of tired eyes from using a computer or other digital device

A non-inferiority margin of 10% will be used.

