14.4. Level of Statistical Significance

All co-primary safety, co-primary efficacy, and secondary hypotheses will be tested using a multibranch gate keeping strategy. Study hypotheses will be evaluated sequentially as follows:

Clinical Study Protocol

CR-6521, v 3.0

■

JJVC CONFIDENTIAL

Clinical Study Protocol
Johnson & Johnson Vision Care, Inc.

First, co-primary safety hypotheses will be evaluated using 95% central posterior credible intervals for the probability of grade 3 or higher SLFs and acceptable lens fitting. Both hypotheses must be met in order to test co-primary efficacy hypotheses. Each co-primary efficacy hypothesis will be tested with a type I error rate of 5%. All co-primary safety and co-primary efficacy hypotheses must be met to test any secondary hypotheses. Secondary hypotheses will be tested utilizing a Bonferroni adjustment¹⁰ with an overall two-sided family-wise type I error rate of 5% (2.5% individually).

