14.6. Secondary Analysis

CLUE Handling and Comfort Scores

CLUE Handling and Comfort scores after 1-week of lens wear will be analyzed separately using a linear mixed model adjusting for baseline scores as a covariate. Sequence of lens wear, lens type and period will be included in the model as fixed effects. Subject characteristics such as, gender, age and/or cylinder power made be included in the model if appropriate. Site ID will be included in the model as a random effect (G-side). The residual error between measurements within the same subject will be modeled using an unstructured (UN) covariance structure. If the model fails to converge with a UN covariance, then a compound systemic (CS) covariance structure will be used. The Kenward and Roger Method will be used for the denominator degrees of freedom.¹¹ CLUE Handling and Comfort scores for each study lens will be estimated using 97.5% confidence intervals (CI) constructed for the least-square means (LSM).

Secondary Hypothesis 1:

The null and alternative hypothesis to test for superiority of CLUE Handling score for the test lens relative to the threshold 61 are as follows:

$$\begin{aligned} H_0: \mu_{TTTTTTTT} &\leq 61 \\ H_A: \mu_{TTTTTTTT} &> 61 \end{aligned}$$

Where $\mu_{TTTTTTTT}$, represents the population mean for test lens after 1 week of lens wear with respect to CLUE Handling scores. Superiority will be declared if the lower limit of the 97.5% CI is above 61.

Secondary Hypothesis 2:

The null and alternative hypothesis to test for superiority of CLUE Comfort score for the test lens relative to the threshold 58 are as follows:

$$\begin{aligned} H_0: \mu_{TTTTTTTT} &\leq 58 \\ H_A: \mu_{TTTTTTTT} &> 58 \end{aligned}$$

Where $\mu_{TTTTTTTT}$, represents the population mean for test lens after 1 week of lens wear with respect to CLUE comfort scores. Superiority will be declared if the lower limit of the 97.5% CI is above 58.

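### Secondary power in section 14.2 does not follow from its own inputs: at n=135 Table 8 gives about 66% for CLUE Handling and above 99.9% for Comfort, against 97% each in Table 9 and 99% each in the text

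*Combined protocol and SAP*

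**What the plan says.** Section 14.2 sizes CLUE Handling and CLUE Comfort separately with a "one-sided, one-sample mean t-test, with a type I error rate of 2.5% for each hypothesis". It then states "To preserve the overall study power, each endpoint was powered to 99" percent. In the paragraph above Table 9 it adds that "secondary endpoints were powered to achieve at least 99% statistical power", and argues that this has "minimal impact on overall study power because of the multibranch gate keeping approach being implemented".

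The two tables in the same section give:

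| Endpoint | Table 8 mean (SD) | Threshold | Table 9 n | Table 9 power |
|---|---|---|---|---|
| Handling | 65.4 (21.50) | 61 | 135 | 97% |
| Comfort | 67.9 (21.50) | 58 | 135 | 97% |

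The thresholds of 61 and 58 are the same in sections 2.3 and 14.6 and in Table 9.

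The decision level is worded in three further places. Section 14.4 tests the secondary hypotheses by Bonferroni "with an overall two-sided family-wise type I error rate of 5% (2.5% individually"). Section 14.6 gives the rules "Superiority will be declared if the lower limit of the 97.5% CI is above 61" (Handling) and "Superiority will be declared if the lower limit of the 97.5% CI is above 58" (Comfort). Section 2.3 says that the mean Handling score "will be greater than 61 points with 95% statistical confidence", and words Comfort the same way with 58.

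**The concern.** Three things do not fit together. First, the text says 99% and Table 9 says 97% for the same two endpoints; that needs no calculation. Second, with equal SDs and equal n, gaps of 4.4 and 9.9 points cannot both give 97% power. Third, the sizing uses one-sided 2.5%, but a two-sided 97.5% interval leaves only 1.25% in the favourable tail.

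The secondary objective in section 2.1 is to demonstrate that the lens meets user needs for handling and comfort. A reader who believes that power is 97% to 99% will take a miss on Handling as evidence that the need is unmet. If power is really two in three or three in four, a miss says much less. If instead Table 8 or a threshold is misprinted, then a historical input or a pass/fail criterion is wrong, which is at least as serious.

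**Working it through.** **Inputs.** Means, SDs and thresholds are as tabulated above. The sizing alpha is one-sided 2.5% (section 14.2). The decision level is the lower limit of a 97.5% CI (section 14.6), which is one-sided 1.25% if the interval is two-sided. Sample sizes are n=135 (Table 9) and the completion target of 165.

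**Formula.** The one-sample t-test has df = n−1 and noncentrality ncp = (mean − threshold)/SD × √n. Power = P(T′ > t_crit), where T′ is noncentral t with that df and ncp.

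**Does the formula reproduce Table 9 elsewhere?**
- Visual acuity, n=9, one-sided 5%: gap 0.115, SD 0.0769, power 99.2% (Table 9: 99%).
- CLUE Vision, n=144: gap 67.4 − 62 = 5.4, SD 19.67, power 90.5% at one-sided 2.5% (Table 9: 91%). The one-sided 5% named in the text for that endpoint would give 94.9%.

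So the method is not the source of the mismatch.

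**Secondary endpoints at n=135 and one-sided 2.5% (t_crit = 1.978).**
- Handling: ncp = 4.4/21.5 × √135 = 2.378; power **65.6%**. Normal check: Φ(2.378 − 1.960) = 66.2%.
- Comfort: ncp = 9.9/21.5 × √135 = 5.350; power **99.96%**.

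Table 9's 97% is reproduced for neither. Handling also fails the text's 99%. Comfort meets it and conflicts only with Table 9.

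**Both levels and both sample sizes.**

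| | n=135, 2.5% | n=135, 1.25% | n=165, 2.5% | n=165, 1.25% |
|---|---|---|---|---|
| Handling (gap 4.4) | 65.6% | 54.5% | 74.3% | 64.3% |
| Comfort (gap 9.9) | 99.96% | 99.89% | >99.9% | >99.9% |

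**Could another alpha explain 97% for Handling at n=135?** No. One-sided 5% gives 76.5% and one-sided 10% gives 86.2%.

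**What would be needed?**
- Handling n at one-sided 2.5%: 355 for 97% and 441 for 99%. At 1.25%: 409 and 501.
- Comfort n at one-sided 2.5%: 72 for 97% and 89 for 99%, not 135.
- For Handling to have 97% at n=135 and one-sided 2.5%: a gap of 7.16 instead of 4.4, or an SD of 13.2 instead of 21.5.

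**Possible sources of the 97%.** Suppose the means or thresholds were crossed. At n=135 and one-sided 2.5%, 65.4 against 58 (gap 7.4) gives 97.8%, and 67.9 against 61 (gap 6.9) gives 95.9%. Both are near 97% but neither equals it. The average of the two Table 8 gaps, (4.4 + 9.9)/2 = 7.15, gives 97.0%. Neither explanation can be proved from the documents. The crossed pairing would not support 99% for each endpoint even at n=165: it gives 99.3% and 98.4% at one-sided 2.5%, and 98.4% and 96.8% at 1.25%.

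**The case against.** The arithmetic is not in dispute; the case on the other side concerns scope and weight.

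- **Comfort satisfies the text.** At 99.96% it does meet 99%. This stands: the 99% claim fails through Handling.
- **The alpha mismatch is an assumption.** Section 14.6 does not give the sidedness of its 97.5% interval, whereas section 14.7 does for its own. A one-sided 97.5% bound would match the sizing alpha. This stands as a qualification, although section 14.4's two-sided wording favours the two-sided reading. On that reading the rule is stricter than the sizing, so type I error is not inflated and only power suffers.
- **The planned model differs.** Section 14.6 adjusts for baseline, which could improve precision. That is true, but section 14.2 sizes on an unadjusted t-test and documents no baseline correlation. An effective SD near 13.2 would be needed to rescue 97% for Handling at n=135.
- **The crossed pairing is speculative.** Agreed; it is only a reason to check the sources.
- **The secondaries do not drive the trial.** CLUE Vision sets the 144, the 165 allows for a later meta-analysis, and gatekeeping leaves the co-primary power of about 86% untouched. All correct. But gatekeeping does not make the stated secondary power true, and the plan offers that power as support for its secondary tests.

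**Conclusion.** The concern holds. Table 8, Table 9 and the text of section 14.2 cannot all be right for the secondary endpoints, and the documents do not show which is wrong.

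If Table 8 is right, the chance of missing Handling at 165 completers is 100 − 74.3 = about 26% at one-sided 2.5%, or 100 − 64.3 = about 36% under a two-sided 97.5% CI. At the n=135 for which Table 9 states its power, it is 34% or 45% (100 − 65.6, 100 − 54.5), against the 1% to 3% implied. Comfort is powered above 99% in every case.

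These figures assume the Table 8 means and SDs, the unadjusted one-sample t-test used for sizing, and that the co-primary gate has been passed. The lower Handling figure at each n also assumes that the 97.5% interval is two-sided. The co-primary power is not affected.

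**What to change.** 1. Check the Handling and Comfort means and SDs in Table 8, and the 61 and 58 thresholds, against their sources, including whether a mean or a threshold was crossed or one common gap was used for both.
2. Settle one decision level for each secondary hypothesis and word sections 2.3, 14.2, 14.4 and 14.6 to it. State whether the 97.5% interval is two-sided, and whether the 95% confidence in section 2.3 is family-wise or applies to each hypothesis.
3. Recompute secondary power at that level and restate Table 9. If Table 8 stands, give Handling at 165 completers as about 64% (two-sided 97.5% CI) or about 74% (one-sided 2.5%), labelled as unadjusted t-test values, and Comfort as above 99%. If an input or threshold proves wrong, correct it and give the recomputed values.
4. Delete both statements that the secondary endpoints are powered to 99% or more.

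The cost is a source check and edits to text and tables. Sample size, visits and conduct stay as they are. If Table 8 stands, the stated Handling power becomes visibly less favourable.

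### The ~88% combined efficacy power multiplies powers taken at four different sample sizes; at the trial's own 144 or 165 completers it equals the CLUE Vision power, about 91% or 94%

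*Combined protocol and SAP*

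**What the plan says.** Section 14.2 gives three of the four co-primary efficacy hypotheses a power of about 99% and CLUE Vision 91%, "which provided a combined power of ~88%. Therefore, the overall combined study power for co-primary safety and co-primary efficacy hypotheses is ~86" per cent. The second figure follows from multiplying by a safety power of about 98%. The plan treats the result as adequate support for the study's conclusions.

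Table 9 gives a sample size and a power for each co-primary efficacy row:

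- Visual acuity: "Superiority (0.00) 9 99"
- Absolute rotation within 10 degrees: "Statistically greater than (80%) 40 99"
- Stability with blinks within 5 degrees: "Statistically greater than (80%) 100 99"
- CLUE Vision: 144 subjects, 91%

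Below the table the plan says: "While only a total of 144 subjects are required to complete the study based on the sample size calculations". It sets the completion target at 165 or more. No combined power is given at either size. Section 2.3 requires every co-primary hypothesis to be met.

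On alpha, the overview in Section 14.2 gives a two-sided 5% rate for the efficacy endpoints, and Section 14.5 declares success on a 95% confidence limit. The paragraph in Section 14.2 that describes the acuity and CLUE Vision calculations gives a one-sided test at 5%.

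**The concern.** The probability that four tests all succeed in one trial has to be built from the four powers at that trial's size. Multiplying a power at 9 subjects by one at 40, one at 100 and one at 144 does not give this. The plan relies on the result, so it should be the figure for the trial that will be run. It also matters which endpoints carry risk. The product charges one point each to acuity, orientation and stability, although at the planned size these contribute almost nothing and only CLUE Vision matters.

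**Working it through.** **Inputs.** From Table 8: acuity mean -0.115, SD 0.0769; CLUE Vision mean 67.4, SD 19.67. From Section 14.2: orientation rate 97.5%, stability rate 98%, between-eye correlation 0.70. Thresholds are 0.00 logMAR, 80%, 80% and 62. Sizes are in completers, so the 10% dropout allowance is not applied.

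**The plan's own figures.** Efficacy: 0.99^3 x 0.91 = 0.883. Safety: 0.99^2 = 0.980. Overall: 0.99^5 x 0.91 = 0.865. All three match the text.

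**CLUE Vision.** One-sample t-test, power = 1 - F(t(1-alpha, n-1)), where F is the noncentral t distribution with n-1 degrees of freedom and noncentrality (67.4 - 62)/19.67 x sqrt(n) = 0.2745 x sqrt(n).

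| n | noncentrality | one-sided 2.5% | one-sided 5% |
|---|---|---|---|
| 144 | 3.29 | 90.5% | 94.9% |
| 165 | 3.53 | 93.9% | 96.9% |

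The normal approximation at one-sided 2.5% gives 90.9% and 94.1%. Only one-sided 2.5%, the equivalent of the 95% interval rule, reproduces Table 9's 91% at 144.

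**Acuity.** Noncentrality is 0.115/0.0769 x sqrt(n) = 1.495 x sqrt(n). At n = 9 the power is 99.2% at one-sided 5% and 97.4% at one-sided 2.5%. At 144 and 165 it is 100% to four decimals under either alpha. Table 9's acuity row thus fits one-sided 5% better, while its CLUE Vision row fits only 2.5%.

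**Orientation and stability.** These used the correlated-binomial model by which Section 14.2 sizes them. Outcomes were enumerated, the posterior was computed on a grid with the Section 14.5 priors, and success meant a lower 95% credible limit above 80%.

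| n | orientation, 97.5% | stability, 98% |
|---|---|---|
| 40 | 99.4% | 99.7% |
| 100 | ~100% | ~100% |
| 144 | ~100% | ~100% |
| 165 | ~100% | ~100% |

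Section 14.5 analyses these two endpoints with a logistic mixed model instead. A rough check that does not use the Bayesian model: 288 eyes with a design effect of 1.70 are worth 288/1.70 = 169 independent eyes. The standard error is sqrt(0.8 x 0.2/169) = 0.031 at the threshold and sqrt(0.975 x 0.025/169) = 0.012 at the assumed rate. Then (0.175 - 1.96 x 0.031)/0.012 is about 9.5, so power is still essentially 100%.

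**Combined efficacy power at one size.** At 144: 1.000 x 1.000 x 1.000 x 0.905 = 90.5%. At 165: 93.9%. With one-sided 5%: 94.9% and 96.9%. Because three factors are essentially 1, independence between endpoints is not needed.

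**The safety factor.** The ~98% comes from two rows at 100 subjects. Lens fit at a 99% rate gives essentially 100% at 100 and at 144. Slit-lamp findings, in a test-lens-only version of the same model with an upper 95% credible limit below 5%, give:

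| n | 2% rate (the plan's reference), correlation 0.70 | 1% rate, same correlation |
|---|---|---|
| 100 | about 55% | about 84% |
| 144 | about 62-63% | about 93% |
| 165 | about 73-74% | about 97% |

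Table 9 gives 99% at 100.

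**The case against.** The strongest defence is that ~88% is a floor. Section 14.2 speaks of minimum power, and of at least 99% for orientation and stability, and a product of minimums errs on the safe side. This stands as to direction: the figure understates efficacy power, and nothing here shows an underpowered efficacy analysis. But the text presents the product as the combined power, not as a bound.

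Four stronger readings are tempting, and the documents do not support them.

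- That no trial has 88% power. About 133 to 135 completers would give 88.2% to 88.6%. That is simply not a size the plan uses for its co-primary endpoints.
- That the plan conceals its dependence on CLUE Vision. The paragraph names CLUE Vision as the exception at 91%, and Table 9 shows it. What is missing is the statement that at the planned size it is the only efficacy endpoint that matters.
- That Table 9 contradicts itself on stability. The plan says "Sample size estimates for toric lens orientation and rotational stability were calculated using the same technique", yet lists 100 subjects for the easier 98% rate and 40 for the harder 97.5%. If 100 is only the size simulated and 99% is a floor, both entries can be true. The column then mixes minimum sizes with simulated ones, which is a matter of labelling.
- That overall power rises to about 89% or 92% (0.98 x 0.905 = 0.887; 0.98 x 0.939 = 0.920). This repeats the fault, since the 98% belongs to 100 subjects, and the slit-lamp check suggests that this factor is too high.

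**Conclusion.** The concern holds for the efficacy component. On the plan's inputs, combined efficacy power is the CLUE Vision power: about 91% at 144 completers and 94% at 165 under the 95% interval rule, against ~88% stated. The understatement is about 3 and 6 points. Under the one-sided 5% in the calculation paragraph the figures are about 95% and 97%, and the gap is wider.

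This assumes the Table 8 means and SDs, a one-sample t-test in place of the planned mixed model, and test-lens data from every completer. The last would fail if the first-period-only fallback in Section 4.2 were used.

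The error is conservative and changes no enrolment number, threshold or decision rule, so it is a minor reporting correction. No replacement for the overall ~86% is supported yet. The slit-lamp figures come from a simplified model and the plan's pessimistic 2% rate (Table 8 reports 0%), so they are a reason to rerun the safety rows, not a new overall figure.

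**What to change.** 1. Recompute every row of Table 9, safety rows included, at common sizes of 144 and 165. Put the per-row minimum n in a separate column and mark any n that is only the simulated size.
2. Restate combined efficacy power as about 91% (144) or 94% (165), and say that CLUE Vision determines it.
3. Reconcile the one-sided 5% in the acuity and CLUE Vision paragraph of Section 14.2 with the two-sided 5% in its overview and the 95% interval rules in Section 14.5.
4. Recompute the overall figure only after the safety rows have been rerun at the common size. Report the slit-lamp power with its assumed rate and correlation.

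The efficacy correction costs a rerun of existing calculations and edits to one table and a few sentences of Section 14.2, with no change to enrolment. Whether the safety rerun has further consequences depends on its result.
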